### **7.2.2 Reporting of Pregnancy and Lactation to the Sponsor**

Although pregnancy and lactation are not considered adverse events, it is the responsibility of investigators or their designees to report any pregnancy or lactation in a subject (spontaneously reported to them) that occurs during the trial.

Pregnancies and lactations that occur after the consent form is signed but before treatment allocation/randomization must be reported by the investigator if they cause the subject to be excluded from the trial, or are the result of a protocol-specified intervention, including but not limited to washout or discontinuation of usual therapy, diet, placebo treatment or a procedure. Pregnancies and lactations that occur from the time of treatment allocation/randomization through 120 days following cessation of Sponsor's product, or 30 days following cessation of trial treatment if the subject initiates new anticancer therapy, whichever is earlier, must be reported by the investigator. All reported pregnancies must be followed to the completion/termination of the pregnancy. Pregnancy outcomes of spontaneous abortion, missed abortion, benign hydatidiform mole, blighted ovum, fetal death, intrauterine death, miscarriage and stillbirth must be reported as serious events

(Important Medical Events). If the pregnancy continues to term, the outcome (health of infant) must also be reported.

Such events must be reported within 24 hours to the Sponsor either by electronic media or paper. Electronic reporting procedures can be found in the EDC data entry guidelines. Paper reporting procedures can be found in the Investigator Trial File Binder (or equivalent).

### **7.2.3 Immediate Reporting of Adverse Events to the Sponsor**

#### **7.2.3.1 Serious Adverse Events**

A serious adverse event is any adverse event occurring at any dose or during any use of Sponsor's product that:

- Results in death;
- Is life threatening;
- Results in persistent or significant disability/incapacity;
- Results in or prolongs an existing inpatient hospitalization;
- Is a congenital anomaly/birth defect;
- Is an other important medical event.

**Note:** In addition to the above criteria, adverse events meeting either of the below criteria, although not serious per ICH definition, are reportable to the Sponsor in the same timeframe as SAEs to meet certain local requirements. Therefore, these events are considered serious by the Sponsor for collection purposes.

- Is a new cancer (that is not a condition of the study);
- Is associated with an overdose.

Refer to [Table 14](#) for additional details regarding each of the above criteria.

For the time period beginning when the consent form is signed until treatment allocation/randomization, any serious adverse event, or follow up to a serious adverse event, including death due to any cause other than progression of the cancer under study (reference Section 7.2.3.3 for additional details), that occurs to any subject must be reported within 24 hours to the Sponsor if it causes the subject to be excluded from the trial, or is the result of a protocol-specified intervention, including but not limited to washout or discontinuation of usual therapy, diet, placebo treatment or a procedure.

For the time period beginning at treatment allocation/randomization through 90 days following cessation of trial treatment, or 30 days following cessation of trial treatment if the subject initiates new anticancer therapy, whichever is earlier, any serious adverse event, or follow up to a serious adverse event, including death due to any cause other than progression of the cancer under study (reference Section 7.2.3.3 for additional details), whether or not related to the Sponsor's product, must be reported within 24 hours to the Sponsor either by electronic media or paper. Electronic reporting procedures can be found in the EDC data entry guidelines. Paper reporting procedures can be found in the Investigator Trial File Binder (or equivalent).

Additionally, any serious adverse event, considered by an investigator who is a qualified physician to be related to the Sponsor's product that is brought to the attention of the investigator at any time following consent through the end of the specified safety follow-up period specified in the paragraph above, or at any time outside of the time period specified in the previous paragraph also must be reported immediately to the Sponsor.

All subjects with serious adverse events must be followed up for outcome.

### **7.2.3.2 Events of Clinical Interest**

Selected non-serious and serious adverse events are also known as Events of Clinical Interest (ECI) and must be reported to the Sponsor.

For the time period beginning when the consent form is signed until treatment allocation/randomization, any ECI, or follow up to an ECI, that occurs to any subject must be reported within 24 hours to the Sponsor if it causes the subject to be excluded from the trial, or is the result of a protocol-specified intervention, including but not limited to washout or discontinuation of usual therapy, diet, placebo treatment or a procedure.

For the time period beginning at treatment allocation/randomization through 30 days following cessation of treatment, any ECI, or follow up to an ECI, whether or not related to the Sponsor's product, must be reported within 24 hours to the Sponsor, either by electronic media or paper. Electronic reporting procedures can be found in the EDC data entry guidelines. Paper reporting procedures can be found in the Investigator Trial File Binder (or equivalent).

Events of clinical interest for this trial include:

1. an overdose of Sponsor's product, as defined in Section 7.2.1 - Definition of an Overdose for This Protocol and Reporting of Overdose to the Sponsor, that is not associated with clinical symptoms or abnormal laboratory results.
2. an elevated AST or ALT lab value that is greater than or equal to 3X the upper limit of normal and an elevated total bilirubin lab value that is greater than or equal to 2X the upper limit of normal and, at the same time, an alkaline phosphatase lab value that is less than 2X the upper limit of normal, as determined by way of protocol-specified laboratory testing or unscheduled laboratory testing.\*

\*Note: These criteria are based upon available regulatory guidance documents. The purpose of the criteria is to specify a threshold of abnormal hepatic tests that may require an additional evaluation for an underlying etiology. The trial site guidance for assessment and follow up of these criteria can be found in the Investigator Trial File Binder (or equivalent).

### **7.2.3.3 Protocol-Specific Exceptions to Serious Adverse Event Reporting**

Efficacy endpoints as outlined in this section will not be reported to the Sponsor as described in Section 7.2.3.

Specifically, the suspected/actual events covered in this exception include any event that is disease progression of the cancer under study.

The Sponsor will monitor unblinded aggregated efficacy endpoint events and safety data to ensure the safety of the subjects in the trial. Any suspected endpoint which upon review is not progression of the cancer under study will be forwarded to global safety as an SAE within 24 hours of determination that the event is not progression of the cancer under study.

#### **7.2.4 Evaluating Adverse Events**

An investigator who is a qualified physician will evaluate all adverse events according to the NCI Common Terminology for Adverse Events (CTCAE), version 4.0. Any adverse event which changes CTCAE grade over the course of a given episode will have each change of grade recorded on the adverse event case report forms/worksheets.

All adverse events regardless of CTCAE grade must also be evaluated for seriousness.

For studies in which multiple agents are administered as part of a combination regimen, the investigator may attribute each adverse event causality to the combination regimen or to a single agent of the combination. In general, causality attribution should be assigned to the combination regimen (i.e., to all agents in the regimen). However, causality attribution may be assigned to a single agent if in the investigator's opinion, there is sufficient data to support full attribution of the adverse event to the single agent.

Table 14 Evaluating Adverse Events

An investigator who is a qualified physician, will evaluate all adverse events as to:

V4.0 CTCAE Grading	Grade 1	Mild; asymptomatic or mild symptoms; clinical or diagnostic observations only; intervention not indicated.
	Grade 2	Moderate; minimal, local or noninvasive intervention indicated; limiting age-appropriate instrumental ADL.
	Grade 3	Severe or medically significant but not immediately life-threatening; hospitalization or prolongation of hospitalization indicated; disabling; limiting self-care ADL.
	Grade 4	Life threatening consequences; urgent intervention indicated.
	Grade 5	Death related to AE
Seriousness	A serious adverse event is any adverse event occurring at any dose or during any use of Sponsor's product that:	
	† Results in death ; or	
	† Is life threatening ; or places the subject, in the view of the investigator, at immediate risk of death from the event as it occurred (Note: This does not include an adverse event that, had it occurred in a more severe form, might have caused death.); or	
	† Results in a persistent or significant disability/incapacity (substantial disruption of one's ability to conduct normal life functions); or	
	† Results in or prolongs an existing inpatient hospitalization (hospitalization is defined as an inpatient admission, regardless of length of stay, even if the hospitalization is a precautionary measure for continued observation. (Note: Hospitalization for an elective procedure to treat a pre-existing condition that has not worsened is not a serious adverse event. A pre-existing condition is a clinical condition that is diagnosed prior to the use of a Merck product and is documented in the patient's medical history.); or	
	† Is a congenital anomaly/birth defect (in offspring of subject taking the product regardless of time to diagnosis); or	
	Is a new cancer (that is not a condition of the study) (although not serious per ICH definition, is reportable to the Sponsor within 24 hours to meet certain local requirements); or	
	Is an overdose (whether accidental or intentional). Any adverse event associated with an overdose is considered a serious adverse event for collection purposes. An overdose that is not associated with an adverse event is considered a non-serious event of clinical interest and must be reported within 24 hours.	
	Other important medical events that may not result in death, not be life threatening, or not require hospitalization may be considered a serious adverse event when, based upon appropriate medical judgment, the event may jeopardize the subject and may require medical or surgical intervention to prevent one of the outcomes listed previously (designated above by a †).	
Duration	Record the start and stop dates of the adverse event. If less than 1 day, indicate the appropriate length of time and units	
Action taken	Did the adverse event cause the Sponsor's product to be discontinued?	
Relationship to Sponsor's Product	Did the Sponsor's product cause the adverse event? The determination of the likelihood that the Sponsor's product caused the adverse event will be provided by an investigator who is a qualified physician. The investigator's signed/dated initials on the source document or worksheet that supports the causality noted on the AE form, ensures that a medically qualified assessment of causality was done. This initialed document must be retained for the required regulatory time frame. The criteria below are intended as reference guidelines to assist the investigator in assessing the likelihood of a relationship between the test drug and the adverse event based upon the available information. The following components are to be used to assess the relationship between the Sponsor's product and the AE ; the greater the correlation with the components and their respective elements (in number and/or intensity), the more likely the Sponsor's product caused the adverse event (AE):	
	Exposure	Is there evidence that the subject was actually exposed to the Sponsor's product such as: reliable history, acceptable compliance assessment (pill count, diary, etc.), expected pharmacologic effect, or measurement of drug/metabolite in bodily specimen?
	Time Course	Did the AE follow in a reasonable temporal sequence from administration of the Sponsor's product? Is the time of onset of the AE compatible with a drug-induced effect (applies to trials with investigational medicinal product)?
	Likely Cause	Is the AE not reasonably explained by another etiology such as underlying disease, other drug(s)/vaccine(s), or other host or environmental factors

Relationship to Sponsor's Product (continued)	The following components are to be used to assess the relationship between the test drug and the AE: (continued)	
	Dechallenge	Was the Sponsor's product discontinued or dose/exposure/frequency reduced? If yes, did the AE resolve or improve? If yes, this is a positive dechallenge. If no, this is a negative dechallenge. (Note: This criterion is not applicable if: (1) the AE resulted in death or permanent disability; (2) the AE resolved/improved despite continuation of the Sponsor's product; or (3) the trial is a single-dose drug trial); or (4) Sponsor's product(s) is/are only used one time.)
	Rechallenge	Was the subject re-exposed to the Sponsor's product in this study? If yes, did the AE recur or worsen? If yes, this is a positive rechallenge. If no, this is a negative rechallenge. (Note: This criterion is not applicable if: (1) the initial AE resulted in death or permanent disability, or (2) the trial is a single-dose drug trial); or (3) Sponsor's product(s) is/are used only one time). NOTE: IF A RECHALLENGE IS PLANNED FOR AN ADVERSE EVENT WHICH WAS SERIOUS AND WHICH MAY HAVE BEEN CAUSED BY THE SPONSOR'S PRODUCT, OR IF REEXPOSURE TO THE SPONSOR'S PRODUCT POSES ADDITIONAL POTENTIAL SIGNIFICANT RISK TO THE SUBJECT, THEN THE RECHALLENGE MUST BE APPROVED IN ADVANCE BY THE SPONSOR CLINICAL DIRECTOR AS PER DOSE MODIFICATION GUIDELINES IN THE PROTOCOL.
	Consistency with Trial Treatment Profile	Is the clinical/pathological presentation of the AE consistent with previous knowledge regarding the Sponsor's product or drug class pharmacology or toxicology?
The assessment of relationship will be reported on the case report forms /worksheets by an investigator who is a qualified physician according to his/her best clinical judgment, including consideration of the above elements.		
Record one of the following	Use the following scale of criteria as guidance (not all criteria must be present to be indicative of a Sponsor's product relationship).	
Yes, there is a reasonable possibility of Sponsor's product relationship.	There is evidence of exposure to the Sponsor's product. The temporal sequence of the AE onset relative to the administration of the Sponsor's product is reasonable. The AE is more likely explained by the Sponsor's product than by another cause.	
No, there is not a reasonable possibility of Sponsor's product relationship	Subject did not receive the Sponsor's product OR temporal sequence of the AE onset relative to administration of the Sponsor's product is not reasonable OR the AE is more likely explained by another cause than the Sponsor's product. (Also entered for a subject with overdose without an associated AE.)	

### 7.2.5 Sponsor Responsibility for Reporting Adverse Events

All Adverse Events will be reported to regulatory authorities, IRB/IECs and investigators in accordance with all applicable global laws and regulations, i.e., per ICH Topic E6 (R1) Guidelines for Good Clinical Practice.

## 8.0 STATISTICAL ANALYSIS PLAN

This section outlines the statistical analysis strategies and procedures for the primary and key secondary analyses of the study. Exploratory and other non-confirmatory analyses will be outlined in a separate supplemental Statistical Analysis Plan (sSAP).

If, after the study has begun, changes are made to primary and/or secondary objectives, or the statistical methods related to those objectives, then the protocol will be amended (consistent with ICH Guideline E9). Changes to exploratory or other non-confirmatory analyses made after the protocol has been finalized, but prior to the conduct of any analyses, will be documented in the sSAP as needed and referenced in the Clinical Study Report (CSR) for the study. Post hoc exploratory analyses will be clearly identified in the CSR.

### 8.1 Statistical Analysis Plan Summary

This section contains a brief summary of the statistical analyses for this trial. Full details are in the Statistical Analysis Plan (SAP), Section 8.2 through 8.12.

Trial Design Overview	Phase 1b/II trial of preladenant as monotherapy and preladenant in combination with pembrolizumab in subjects with advanced solid tumors. The trial applies an mTPI design for dose escalation and confirmation of RP2Ds, followed by an expansion phase to further examine safety and exploratory efficacy in select tumor types.
Analysis Populations	Safety (Primary): All-Subjects-as-Treated (ASaT) Efficacy (Secondary & Exploratory): Full Analysis Set (FAS)
Primary Endpoint(s)	Safety: Dose-limiting toxicities (DLTs)
Key Secondary Endpoints	ORR in subjects treated with preladenant as monotherapy and preladenant in combination with pembrolizumab
Statistical Methods for Key Efficacy/Immunogenicity/ Pharmacokinetic Analyses	The point estimate and 95% confidence interval (CI) for ORR will be evaluated separately in subjects treated with preladenant as monotherapy and subjects treated with preladenant in combination with pembrolizumab, using exact binomial distribution.
Treatment Assignment	Subjects will be allocated to receive single agent preladenant or preladenant co-administered with pembrolizumab centrally through an IVRS/IWRS. In Part 1, subjects will be allocated by non-random assignment. Allocation will alternate between the 2 arms when both arms are open for enrollment. In Part 2, subjects will be allocated to each cohort by tumor type. . The trial is open-label.
Statistical Methods for Key Safety Analyses	Summary statistics (counts, percentages, means, standard deviations, etc.) will be provided for the safety endpoints as appropriate. The pool-adjacent-violators algorithm [22] that forces the DLT rate estimates to be non-decreasing with dose levels and pools adjacent violators for weighted estimates by sample size will be used to estimate the DLT rates across doses. The estimates of the DLT rates among subjects treated at the RP2Ds of preladenant when used as monotherapy and when used in combination with pembrolizumab and the 80% Bayesian credible intervals for the estimates will be provided.

Interim Analyses	Data will be examined on a continuous basis to allow for dose escalation and confirmation decisions using the mTPI design in Part 1. An interim futility check will be performed for each of the select solid tumor cohorts in Part 2.
Multiplicity	No multiplicity adjustment is planned for this Phase 1b/II trial.
Sample Size and Power	The overall sample size for this trial depends on the observed DLT profiles of preladenant as monotherapy and preladenant in combination with pembrolizumab. A target sample size of 112 subjects will be used for trial planning purposes.

## 8.2 Responsibility for Analyses/In-House Blinding

The statistical analyses of the data obtained from this trial will be the responsibility of the Clinical Biostatistics department of the Sponsor.

The trial is open-label, i.e., subjects, investigators, and Sponsor personnel will be aware of subject treatment assignment after each subject is enrolled and treatment is assigned.

## 8.3 Hypotheses/Estimation

Objectives and hypotheses of the study are outlined in Section 3.0.

## 8.4 Analysis Endpoints

### 8.4.1 Efficacy/Immunogenicity/Pharmacokinetic Endpoints

Overall response rate is a secondary endpoint of the trial. Overall response rate is defined as the proportion of subjects in the analysis population who experience complete response (CR) or partial response (PR) using RECIST 1.1 criteria as assessed by investigator review. Other efficacy endpoints (e.g., DOR, PFS) are exploratory endpoints in this trial and will be defined in the sSAP.

Pharmacokinetic endpoints include serum concentrations of preladenant and pembrolizumab and derived PK parameters.

### 8.4.2 Safety Endpoints

The primary safety endpoint is the rate of DLTs. A description of safety measures is provided in Section 5.2.2 and Section 7.2.

## 8.5 Analysis Populations

### 8.5.1 Safety Analysis Population

The All-Subjects-as-Treated (ASaT) population will be used for the analysis of safety data in this study. The ASaT population consists of all subjects who received at least one dose of study treatment. In case of treatment administration errors, subjects will be analyzed according to the treatment they actually received. For DLT evaluation, ASaT subjects that were observed for safety for 21 days after the first dose of assigned treatment or experienced a DLT prior to 21 days after the first dose of assigned treatment will be used. The replacement subjects will also be considered evaluable if the above specified criteria are met.

At least one laboratory or vital sign measurement obtained subsequent to at least 1 dose of study treatment is required for inclusion in the analysis of each specific parameter. To assess change from baseline, a baseline measurement is also required. Safety data from subjects who experienced disease progression in the monotherapy arm and crossed over into the combination arm will be presented separately.

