### **5.2.2.1 Replacement of Subjects in DLT Period**

In order to fully evaluate the safety of the combination therapy in this study, all subjects enrolled must meet the criteria for evaluability for Cycle 1. Subjects are considered non-evaluable and will be replaced if:

- They are enrolled but not treated,
- They discontinue from the trial prior to completing all safety evaluations due to reasons other than drug-related AEs,
- They received <90% of the total pembrolizumab infusion in Cycle 1 (e.g., because the infusion had to be discontinued due to an infusion reaction) and did not experience a drug-related event,
- They received  $\leq 75\%$  of preladenant doses intended for the trial during Cycle 1 and did not experience a drug-related AE,
- They must take a prohibited concomitant medication during Cycle 1, unless this medication is used to treat a study drug-related AE,
- They must undergo medical / surgical procedures or have logistical issues not related to study therapy (e.g., elective surgery, unrelated medical events) during Cycle 1.

Non-evaluable subjects will not be counted toward the cohort total for DLT evaluation.

Subjects who experience a DLT in Cycle 1 should be discontinued from treatment. However, if in the opinion of the Investigator, the subject is deriving clinical benefit from the study treatment, the subject may be allowed to continue on the study upon resolution of the DLT to a  $\leq$  Grade 1 adverse event and after discussion with the sponsor.

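### Sections 5.2.2.1, 5.9 and 8.5.1 give three non-identical rules for who counts in DLT evaluation, the denominator of the primary endpoint

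*Combined protocol and SAP*

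**What the plan says.** - **Endpoint.** Sections 8.1 and 8.4.2 make DLTs the primary endpoint. On definitions, 8.4.2 adds only: "A description of safety measures is provided in Section 5.2.2 and Section 7.2".
- **Section 8.5.1 (analysis set).** "For DLT evaluation, ASaT subjects that were observed for safety for 21 days after the first dose of assigned treatment", or who had a DLT before that, are used. It continues: "The replacement subjects will also be considered evaluable if the above specified criteria are met". It does not cite 5.2.2.1 or 5.9.
- **Section 5.2.2.1 (replacement in the DLT period).** Six grounds make a subject non-evaluable. Two are never having been treated, and leaving before the safety evaluations are complete for a reason other than a drug-related AE. The third is less than 90% of the pembrolizumab infusion, for example because the "infusion had to be discontinued due to an infusion reaction) and did not experience a drug-related event". The fourth is 75% or less "of preladenant doses intended for the trial during Cycle 1 and did not experience a drug-related AE". The fifth is "They must take a prohibited concomitant medication during Cycle 1, unless this medication is used to treat a study drug-related AE". The sixth is "They must undergo medical / surgical procedures or have logistical issues not related to study therapy" in Cycle 1. The consequence is: "Non-evaluable subjects will not be counted toward the cohort total for DLT evaluation".
- **Section 5.9 (replacement strategy).** It repeats the first three grounds only, and on the infusion ground it exempts a subject with a DLT rather than one with a drug-related event. It too keeps its non-evaluable subjects out of the cohort count. It replaces them only while the cohort is still accruing, and it refers the reader to 5.2.2.1 for Cycle 1 replacement.
- **Where the count is used.** Section 8.6.2 gives pool-adjacent-violators estimates and 80% credible intervals from a Beta(1,1) prior without naming an evaluable set. The columns of Table 4 count subjects treated.

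**The concern.** All three sections address DLT evaluation, yet a team applying each as written can arrive at different subjects. Sections 5.2.2.1 and 5.9 both control the cohort total that enters Table 4, so where they disagree the escalation denominator is ambiguous. Section 8.5.1 controls the reported estimate, so where it is wider than 5.2.2.1 the published primary endpoint may not rest on the subjects behind the escalation decisions. Under-exposed subjects without a DLT would pull the reported rate down. The trial is open-label, so a choice of denominator left until the data are in would be made with outcomes known. Section 8.0 reserves the supplemental SAP for exploratory and other non-confirmatory analyses, so the primary denominator belongs in this document.

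**Working it through.** **Step 1: the rules side by side.** Every subject below was treated and observed for 21 days.

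| Subject in Cycle 1 | 5.2.2.1 | 5.9 list | 8.5.1, literal |
|---|---|---|---|
| A. Preladenant ≤75%, no drug-related AE, no DLT | out | not listed | in |
| B. Infusion <90%, drug-related event that is not a DLT | in | out | in |
| C. Infusion <90%, no drug-related event | out | out | in |
| D. Prohibited medication not treating a drug-related AE, or unrelated procedure or logistics; no DLT | out | not listed | in |
| E. As D, but with a DLT | out | not listed | in |

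Row B is a direct contradiction between 5.2.2.1 and 5.9. Rows A, C and D are DLT-free subjects whom literal 8.5.1 adds to the 5.2.2.1 set. Row E is the only case in which a DLT is lost from the 5.2.2.1 set but kept in 8.5.1.

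**Step 2: what row A requires.** Cycle 1 has 21 days × 2 doses = 42 doses. 75% of 42 is 31.5, so the ground applies at 31 or fewer doses taken, that is 42 − 31 = 11 or more missed. Missing more than 25% because of drug-related AEs is itself a DLT (Section 5.2.2, item 9), so row A concerns doses missed for other reasons.

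**Step 3: the plan's own figure.** The plan gives no expected DLT rate. The figure that takes this denominator as input is Table 4. With a Beta(1,1) prior, target 30% and margins of 0.03, all 78 cells in rows 0 to 6 are reproduced if a dose is called DU when the posterior probability of a rate above 30% exceeds 0.95. That cutoff is an assumption; the documents do not state it. Rows 7 and 8 were not compared in full because the table text was broken.

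**Step 4: effect on the reported rate.** The counts are assumed, since the documents give no expected number of such subjects. Rate = x/n; posterior = Beta(1 + x, 1 + n − x); 80% interval = 10th to 90th percentile.

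| Set | x/n | Rate | Posterior | 80% interval | Change |
|---|---|---|---|---|---|
| 5.2.2.1 | 4/14 | 28.6% | Beta(5, 11) | 17.2–46.4% | reference |
| 8.5.1, one extra DLT-free subject | 4/15 | 26.7% | Beta(5, 12) | 16.1–43.9% | −1.9 points |
| 8.5.1, two extra | 4/16 | 25.0% | Beta(5, 13) | 15.1–41.6% | −3.6 points |
| 8.5.1, one row E subject | 5/15 | 33.3% | Beta(6, 11) | 21.0–50.4% | +4.8 points |

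These rows assume that each excluded subject is replaced by one without a DLT, so that the 5.2.2.1 set stays at 14. If an excluded subject is not replaced, because accrual has stopped or because the maximum of 14 per dose level (Sections 5.2.1.2 and 8.9) is read as a limit on everyone enrolled, one row A subject gives 4/13 = 30.8% under 5.2.2.1 against 4/14 = 28.6% under 8.5.1. The gap is 2.2 points, of similar size.

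**The case against.** The best defence is that the sections are meant to be read together. Section 5.2.2.1 says without restriction that non-evaluable subjects are not counted for DLT evaluation. Section 8.5.1 speaks of replacement subjects, a notion defined only in 5.2.2.1 and 5.9. Its 21-day clause can therefore be an additional requirement that does not readmit anyone. Likewise, 5.9 points to 5.2.2.1 and may be only a summary.

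Much of this stands. A reader might infer that the plan intends to count both the replaced subject and the replacement. The documents do not say so: the word also in 8.5.1 can mean simply that replacements must meet the same criteria. But the cumulative reading is not written either, and it does not resolve row B. There, applying both lists together would cancel the exemption that 5.2.2.1 grants.

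A reader might also infer that subjects with a DLT are readily lost through the prohibited-medication ground. They are not. That ground spares medication given for a drug-related AE, and a DLT must be judged at least possibly related to study drug, so treating a DLT with a prohibited drug does not exclude the subject. Row E needs an unrelated prohibited drug, procedure or logistical issue in the same cycle as the DLT. Row D is narrowed too: Section 5.5.2 has subjects who need the therapies it lists removed from the trial, and one removed before Day 21 without a DLT fails 8.5.1 as well.

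Finally, the effect is small, no hypothesis is tested, and the estimate closest to 30% only may give a preliminary RP2D, with the totality of the data considered. That limits the consequence but does not remove the inconsistency in a primary-endpoint definition.

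**Conclusion.** The point holds as a conflict between stated rules, and should be fixed. The contradiction between 5.2.2.1 and 5.9 is certain but confined to combination-arm subjects with an incomplete first infusion and a drug-related event short of a DLT; the shorter list in 5.9 is a lesser defect because of its pointer. The divergence of 8.5.1 from 5.2.2.1 follows from a literal reading only. On one or two assumed subjects at a 14-subject dose level, it moves the reported rate down by 1.9 to 3.6 points, or up by 4.8 points in the narrow row E case. All the intervals overlap heavily, and with no discordant subjects the sets are identical.

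A stronger conclusion, that escalation decisions or the RP2D would be wrong, is not supported. The documents give no frequency for these subjects, these shifts alone trigger no decision rule, and the exclusions in 5.2.2.1 and 5.9, not the wider 8.5.1 set, are what remove subjects from the cohort total.

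**What to change.** Reconcile 5.2.2.1 and 5.9 into a single DLT-evaluable definition. The sponsor should choose the exemption wording (DLT, or drug-related event or AE) and state whether a subject with a DLT stays evaluable under every ground; this review takes no position on either. Cite that one set from 5.9, 8.5.1, 8.6.2 and the column heading of Table 4, and use it for the mTPI decisions, the pool-adjacent-violators estimates and the 80% credible intervals. State in 8.5.1 whether a replaced subject is removed. If the sponsor wants to show the literal 8.5.1 set as well, it can be labelled a sensitivity analysis.

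The cost is wording and cross-references in a few places and, depending on the choice made, a slightly smaller reporting denominator and possibly a few more replaced subjects in Part 1.
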